4.3.2. Methods of Contraception

The contraceptive standards and acceptable combinations of contraception methods that are associated with a failure rate of < 1% per year when used consistently and correctly are considered highly effective birth control methods per the Clinical Trial Facilitation Group (CTFG) 2014 guidance document: “*Recommendations related to contraception and pregnancy in clinical trials*”. These methods are detailed in [Table 5](#).

Table 5: Acceptable Methods of Highly Effective Birth Control

 • Combined (estrogen and progestogen containing) hormonal contraception associated with inhibition of ovulation^a: 
 ○ oral ○ intravaginal ○ transdermal • Progestogen-only hormonal contraception associated with inhibition of ovulation^a: 
 ○ oral ○ injectable ○ implantable^b • intrauterine device (IUD)^b • intrauterine hormone-releasing system (IUS)^b • bilateral tubal occlusion^b • vasectomised partner^{b,c} • sexual abstinence^d
--

- a Subjects should not simultaneously use more than one form of hormonal contraception associated with inhibition of ovulation (e.g., if subject is taking oral combined estrogen and progestogen containing hormonal contraception, they should not use another combined estrogen and progestogen or progestogen-only hormonal contraception).
- b Contraception methods that are considered to have low user dependency per the CTFG guidance document.
- c Vasectomised partner is a highly effective birth control method provided that partner is the sole sexual partner of the trial participant and that the vasectomised partner has received medical confirmation of the surgical success.
- d Sexual abstinence is considered a highly effective method only if defined as refraining from heterosexual intercourse during the entire period of risk associated with study treatment. The reliability of sexual abstinence needs to be evaluated in relation to the duration of the clinical trial and the preferred and usual lifestyle of the subject.

Unacceptable methods of contraception for this clinical trial (either because they have a failure rate of > 1% per year or because they are considered unacceptable methods in clinical trials per the CTFG guidance document) are listed in [Table 6](#).

Table 6: Unacceptable Methods of Birth Control

• Progestin-only hormonal contraception	• Male or female condom with or without spermicide
• Cap, diaphragm, or sponge with spermicide	• Periodic abstinence
• Withdrawal	• Spermicides only
• Lactational amenorrhea method (LAM)	• Concomitant use of female and male condoms

4.4. Removal of Subjects From Therapy or Assessment

Jazz Pharmaceuticals or their designee must be notified if a subject is withdrawn from study treatment or from the study. The reason(s) for withdrawal must be documented in the subject’s medical records and CRF.

4.4.1. Treatment Discontinuation

Study treatment may be discontinued for any of the following reasons:

- AE
- Death

- Lost to follow-up
- Withdrawal by subject
- Physician decision (non-AE, non-progressive disease [PD])
- Pregnancy
- PD (either radiographic or unequivocal clinical progression; see [Section 7.2](#))
- Study termination by sponsor
- Other, non-AE

If a subject has not received zanidatamab for more than 4 weeks due to an AE, the investigator should contact the medical monitor to discuss whether the subject should continue to receive study treatment.

If a subject starts subsequent non-study anti-cancer therapy, study treatment must be discontinued before the start of the new therapy.

At a minimum, all efforts should be made for subjects to complete the End of Treatment (EOT) visit ([Section 6.4](#)) and the safety follow-up visit ([Section 6.5](#)).

Subjects who discontinue treatment with zanidatamab for reasons other than progressive disease or start of subsequent anticancer therapy will continue in follow-up with disease assessments approximately every 8 weeks after the previous scan until disease progression or start of subsequent anticancer therapy. Following progression or start of subsequent anticancer therapy, disease assessments will be discontinued, and subjects will enter long-term follow-up for survival status.

4.4.2. Subject Withdrawal from Study

Subjects may be discontinued from the study for any of the following reasons:

- Lost to follow-up
- Death
- Withdrawal of consent
- Study termination by sponsor

5. TREATMENTS

5.1. Treatments Administered

Subjects will be treated with zanidatamab administered as monotherapy.

[figure not shown]
5.2. Investigational Study Drug (Zanidatamab)

Detailed information describing the preparation, administration, and storage of zanidatamab is located in the Pharmacy Manual.

5.2.1. Description

Zanidatamab is a humanized bispecific antibody recognizing 2 non-overlapping epitopes of the ECD of the human HER2 antigen. A schematic representation of zanidatamab is shown in [Figure 2](#). The IgG1-like fragment crystallizable (Fc) region of zanidatamab contains complementary mutations in each constant heavy chain (CH) 3 domain that impart preferential pairing to generate a heterodimeric molecule and correspondingly disfavor formation of homodimers. Chain A is otherwise a normal IgG1 heavy chain and forms a fragment antigen-binding (Fab) arm through pairing with immunoglobulin G (IgG) Kappa light Chain A'. Chain A/A' binds to ECD2 of HER2. Chain B has an IgG1-like hinge and CH2 and CH3 domains, but contains a single-chain variable fragment (scFv) antibody rather than a Fab arm. Chain B binds to ECD4 of HER2. In place of the CH1 domain it has a variable light (VL) domain, an unstructured 20 amino acid linker of glycine and serine residues, followed by a variable heavy (VH) domain to form an scFv domain. Zanidatamab is being developed as a treatment for locally advanced (unresectable) and/or metastatic HER2-expressing cancers.

Figure 2: Structure of Zanidatamab

Fab = fragment antigen-binding; Fc = fragment crystallizable; IgG1 = immunoglobulin G 1; scFv = single-chain variable fragment

5.2.2. Dose and Administration

All subjects must receive prophylactic treatment for potential infusion reactions prior to zanidatamab dosing as outlined in [Section 5.2.7.1](#).

Dosing for zanidatamab will be given as follows:

- 20 mg/kg IV zanidatamab; dosing Q2W on Days 1 and 15 of each 28-day cycle (see [Section 5.2.3](#) for information regarding dose modifications)

Zanidatamab will be administered by IV infusion given over approximately 120 to 150 minutes. If the first 2 doses are well tolerated by a given subject, the infusion duration for that subject may

be decreased to 90 minutes. If the next 2 doses are well tolerated, the infusion duration may be decreased to less than 90 minutes, **however, the infusion rate should not exceed 250 mL/hour**. Refer to the Pharmacy Manual for specific details. Zanidatamab must not be administered as an IV push or bolus. Zanidatamab should not be mixed with other medications. See [Section 5.4](#) for guidelines for management of infusion reactions.

Dosing is based on the subject’s actual body weight at baseline. Doses must be adjusted for subjects who experience a $\geq 10\%$ change in weight from baseline. Other dose adjustments for changes in body weight are permitted per institutional standard. Detailed instructions for dose preparation are provided in the Pharmacy Manual.

5.2.3. Dose Modifications

Recommendations for management of and potential dose modifications for zanidatamab-associated toxicity are provided in [Table 7](#). Guidelines for management of zanidatamab-associated left ventricular dysfunction are provided in [Table 8](#). Guidelines for managing pulmonary toxicity are provided following [Table 8](#).

Note that there must be a minimum of 12 days between doses. Cycles will not be skipped. If a cycle is delayed for any reason, once the subject resumes treatment the next dose delivered will be considered Day 1 of the cycle that was delayed. If the Day 15 dose of a cycle is delayed by ≥ 12 days, then that dose will be considered skipped. The next dose delivered will be Day 1 of the subsequent cycle.

Table 7: Recommended Management and Potential Dose Modifications for Zanidatamab-Associated Toxicity

Adverse Event Related to Zanidatamab	Grade	Action for Zanidatamab
Nausea and/or vomiting	Grade 1/2	
 • Suggest a 5HT3 receptor antagonist until resolution of symptoms. • No dose modification of zanidatamab is required. • For breakthrough nausea or vomiting, consider adding olanzapine 5 or 10 mg daily for three days. For subjects already receiving olanzapine, prochlorperazine may be used.
	Grade 3	
 • Suggest a 5HT3 receptor antagonist plus a glucocorticoid (e. g., dexamethasone); consider adding a NK-1 receptor antagonist to a 5HT3 receptor antagonist and glucocorticoids if the latter combination is not sufficient for symptom relief. Treatment until resolution of symptoms to \leq Grade 1. • Hold zanidatamab until severity \leq Grade 1 or pretreatment level, then resume zanidatamab at the same dose level

Table 7: Recommended Management and Potential Dose Modifications for Zanidatamab-Associated Toxicity (Cont.)

Adverse Event Related to Zanidatamab	Grade	Action for Zanidatamab
Vomiting	Grade 4	
 • Suggest a 5HT3 receptor antagonist plus a glucocorticoid (e. g., dexamethasone); consider adding a NK-1 receptor antagonist to a 5HT3 receptor antagonist and glucocorticoids if the latter combination is not sufficient for symptom relief. Treatment until resolution of symptoms to ≤ Grade 1. • Hold zanidatamab until severity ≤ Grade 1 or pretreatment level. • For Grade 4 vomiting that improves to ≤ Grade 2 within 72 hours with supportive management, resume at the same dose level. • For Grade 4 vomiting lasting longer than 72 hours, permanently discontinue zanidatamab. • For recurrent Grade 4 vomiting, permanently discontinue zanidatamab.
Diarrhea	Grade 1/2	
 • Oral hydration with fluid that contains water, salt, and glucose, such as broth or Gatorade. • Suggest loperamide 4 mg PO followed by 2 mg Q4H or with each loose stool until no diarrhea. • No dose modification of zanidatamab is required.
Diarrhea	Grade 3	
 • Aggressive fluid hydration and clear liquid diet. • Loperamide 4 mg PO followed by 4 mg Q2H until resolution of diarrhea; consider Lomotil alternating with loperamide and/or octreotide 100 or 150 mcg subcutaneously Q8H for subjects with persistent diarrhea despite 48 hours of loperamide. If subjects are refractory to loperamide, Lomotil, and octreotide, gastroenterology should be consulted. • Hold zanidatamab until severity ≤ Grade 1 or pretreatment level. • When symptoms improve to ≤ Grade 1 or pretreatment level, resume zanidatamab at the same dose level or consider dose reduction after discussion with the medical monitor. • For recurrent Grade 3 symptoms despite maximum use of loperamide, Lomotil, and octreotide, zanidatamab dose reduction is mandatory. • For recurrent Grade 3 diarrhea lasting longer than 72 hr despite dose reduction of zanidatamab and maximum use of loperamide, Lomotil, and octreotide, or non-compliance with maximum antidiarrheal therapy, permanently discontinue zanidatamab.
	Grade 4	
 • Aggressive fluid hydration and clear liquid diet. • Loperamide 4 mg PO followed by 4 mg Q2H until resolution of diarrhea; consider Lomotil alternating with loperamide and/or octreotide 100 or 150 mcg subcutaneously Q8H for subjects with persistent diarrhea despite 48 hours of loperamide. If subjects are refractory to loperamide, Lomotil, and octreotide, gastroenterology should be consulted. • Hold zanidatamab until severity ≤ Grade 1 or pretreatment level. • For Grade 4 diarrhea that improves to ≤ Grade 2 within 72 hours with supportive management, resume upon improvement to ≤ Grade 1 or pretreatment level. zanidatamab dose reduction is mandatory. • For Grade 4 diarrhea lasting longer than 72 hours, permanently discontinue zanidatamab. • For recurrent Grade 4 diarrhea, permanently discontinue zanidatamab.

Table 7: Recommended Management and Potential Dose Modifications for Zanidatamab-Associated Toxicity (Cont.)

Adverse Event Related to Zanidatamab	Grade	Action for Zanidatamab
Rash	Grade 1/2	
 Suggest topical steroid as needed. No dose modification of zanidatamab is required.
	Grade 3	
 Suggest initiation of topical steroid; if response insufficient, consider oral corticosteroids. Suggest wound care for skin erosions and ulcerations and to prevent infection. Suggest analgesics for pain control if necessary. If not limiting self-care activities and not associated with infection requiring systemic antibiotics, follow guidelines for Grades 1–2 severity. If limiting self-care activities or associated with infection requiring systemic antibiotics, hold zanidatamab until severity \leq Grade 1 or pretreatment level, then resume at the same dose. For recurrence of Grade 3 symptoms limiting self-care activities or associated with infection requiring systemic antibiotics, despite optimal management with topical and/or oral corticosteroids, zanidatamab dose reduction is mandatory.
	Grade 4	
 Permanently discontinue zanidatamab.
Other zanidatamab-related AEs (other than IRR) ^a	Grade 1/2	
 No dose modification of zanidatamab is required
	Grade 3	
 Hold zanidatamab until severity \leq Grade 1 or pretreatment level. When symptoms improve to \leq Grade 1 or pretreatment level, resume zanidatamab at the same dose level.
	Grade 4	
 Grade 4 electrolyte imbalances/laboratory abnormalities that are not associated with clinical sequelae and are corrected with supplementation/appropriate management within 72 hours of their onset (e.g., Grade 4 hyponatremia) do not require zanidatamab discontinuation. For other Grade 4 AEs, permanently discontinue zanidatamab.

AE = adverse event; IRR = infusion-related reaction; PO = by mouth; Q2H = every 2 hours; Q4H = every 4 hours; Q8H = every 8 hours.

a Guidance for management of infusion-related reactions is provided in [Section 5.2.3.1](#).

Table 8: Management of Left Ventricular Dysfunction

Left Ventricular Dysfunction (Regardless of Causality)	Action for Zanidatamab

 Absolute decrease in LVEF of \geq 16 percentage points from pre-treatment baseline, or LVEF below institutional limits of normal and absolute decrease of \geq 10 percentage points below pretreatment baseline 	
 Suspend dosing for at least 4 weeks Repeat LVEF assessment within 4 weeks Dosing may be resumed within 4 to 8 weeks if LVEF returns to normal limits and the absolute decrease is \leq 15 percentage points from baseline; otherwise, permanently discontinue

 Grade \geq 2 (symptomatic) heart failure 	
 Hold zanidatamab. Referral to a cardiologist is recommended. If symptomatic CHF is confirmed, permanently discontinue.

CHF = congestive heart failure; LVEF = left ventricular ejection fraction.

Pulmonary Toxicity

Dosing with zanidatamab should be held for subjects with symptoms or findings consistent with Grade 2 or higher pneumonitis or interstitial lung disease (ILD) pending evaluation per institutional standards including radiographic imaging and pulmonary function tests as indicated. Zanidatamab treatment should be permanently discontinued in the event of confirmed treatment-related Grade 2 or higher ILD. Subjects who experience any of the above-mentioned pulmonary toxicities should be evaluated for alternative infectious etiology and should receive prompt treatment per local standard of care.

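### The residual row of Table 7 excludes only infusion reactions, so at Grade 3 it says resume where the heart-failure and ILD rules say stop; Grade 2–3 pneumonitis has no explicit stop rule

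*Protocol*

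**What the plan says.** Protocol Section 5.2.3 gives dosing instructions for toxicity in several places. Its opening lines send general toxicity to Table 7, left ventricular dysfunction to Table 8 and pulmonary toxicity to the text after Table 8. They do not say which prevails if two apply.

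- **Table 7, last row**, labelled "Other zanidatamab-related AEs (other than IRR". Grade 1/2: no dose modification is called for. Grade 3: hold, then, once the event is back to Grade 1 or lower "or pretreatment level, resume zanidatamab at the same dose level". Grade 4: apart from promptly corrected laboratory abnormalities, "For other Grade 4 AEs, permanently discontinue zanidatamab". Footnote a reads "Guidance for management of infusion-related reactions is provided in" Section 5.2.3.1 and cites nothing else.
- **Table 8**, headed "Left Ventricular Dysfunction (Regardless of Causality"). For symptomatic heart failure of Grade 2 or higher, dosing is held and cardiology referral is recommended; then "If symptomatic CHF is confirmed, permanently discontinue".
- **Pulmonary Toxicity text.** Hold sentence: "Dosing with zanidatamab should be held for subjects with symptoms or findings consistent with Grade 2 or higher pneumonitis or interstitial lung disease (ILD"); the hold lasts while the event is being worked up. Stop sentence: "Zanidatamab treatment should be permanently discontinued in the event of confirmed treatment-related Grade 2 or higher ILD".

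**The concern.** Heart failure and ILD judged related to the drug are zanidatamab-related events other than infusion reactions, so on its wording the residual row applies to them. A site working from that row would re-dose a subject after a recovered Grade 3 event, whereas the rule written for that event removes the subject from treatment.

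The protocol's own structure makes the incomplete carve-out more noticeable. Section 7.8.2 names three groups of events of special interest: infusion reactions, non-infectious pulmonary toxicities and cardiac events. Section 5.2.3 gives each its own management rule, yet the row excludes only the first. Table 8 applies whatever the cause, while Table 7 covers related events only. Unrelated heart failure therefore meets one rule (stop if confirmed), and drug-related Grade 3 heart failure meets that rule plus one that says resume. The ambiguity falls on the more worrying event.

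At stake are the safety of individual subjects on re-exposure and, secondarily, the counts of dose holds and discontinuations. No efficacy result and no incidence of events of special interest depends on it.

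**Working it through.** **Rules side by side, for drug-related events**

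| Event | Grade | Table 7 residual row | Specific text | Result |
|---|---|---|---|---|
| Heart failure | 2 | No modification required | Hold; permanent stop if confirmed | Inconsistent; the row does not forbid a hold |
| Heart failure | 3 | Hold, then resume at same dose | Hold; permanent stop if confirmed | Contradiction after confirmation |
| Heart failure | 4 | Permanent stop | Hold; permanent stop if confirmed | No conflict |
| ILD | 2 | No modification required | Hold; permanent stop if confirmed as related | Inconsistent; the row does not forbid a hold |
| ILD | 3 | Hold, then resume at same dose | Hold; permanent stop if confirmed as related | Contradiction after confirmation |
| ILD | 4 | Permanent stop | Hold; permanent stop if confirmed as related | No conflict |
| Pneumonitis | 2 | No modification required | Hold; no stop named | No explicit stop |
| Pneumonitis | 3 | Hold, then resume at same dose | Hold; no stop named | No explicit stop; the row's resume is the only explicit next step |
| Pneumonitis | 4 | Permanent stop | Hold; no stop named | No conflict; the row supplies the stop |

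Count: 3 events × 3 grades = 9 = 2 contradictions + 2 inconsistencies + 2 without an explicit stop + 3 without conflict. The pneumonitis lines treat pneumonitis as distinct from ILD; if ILD is read to include it, they become the same as the ILD lines.

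**Does the 4-week contact rule catch a wrong re-dose?** Protocol Section 4.4.1 asks the investigator to contact the medical monitor when a subject has gone more than 4 weeks without drug because of an adverse event. Dosing is every 2 weeks (Section 5.2.2). Take the last dose as Day 0. The Day 14 dose is held and the subject is re-dosed on Day 28. Day 28 is exactly 4 weeks, not more, so no contact is triggered. Counted from the last dose, a delay of up to 28 − 14 = 14 days past the due date escapes the rule. Counted from the missed dose, up to 28 days does.

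**How often could it arise?** The documents give no frequency for related Grade 3 heart failure, ILD or pneumonitis. I assume 0.1% to 1% combined, with the planned n = 100 treated. The expected number is n × p, and the chance of at least one event is 1 − (1 − p)^n:

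- p = 0.1%: expected 0.1; 1 − 0.999^100 = 0.095
- p = 0.5%: expected 0.5; 1 − 0.995^100 = 0.394
- p = 1%: expected 1.0; 1 − 0.99^100 = 0.634

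The first and last reproduce the 0.10 and 0.63 in protocol Table 12 (Section 9.2). They count events, not mis-dosed subjects, who would be fewer.

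**Phase 1 experience (Protocol Section 1.6).** Among 58 subjects, every treatment-related adverse event was Grade 1 or 2, so there were 0 of 58 related events of Grade 3 or higher. The upper limit of the exact two-sided 95% interval is 1 − 0.025^(1/58) = 0.0616, or 6.2%, for related events of any type. The same section reports no treatment-related LVEF decreases of 10% or more.

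**The case against.** The strongest reply is that the section's structure already settles the matter. The opening lines of 5.2.3 direct cardiac and pulmonary events to their own rules, which follow directly after Table 7, and a row headed as a residual is naturally read as covering what has no rule of its own. Infusion reactions sit in a separate subsection that the opening lines do not mention, which may be why only they needed an exclusion and a footnote. Table 7 is also titled as recommended management, while the specific texts direct a permanent stop. This stands as to weight: most sites would probably apply the specific rule. It does not remove the contradiction, because no sentence gives the specific rules precedence.

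A second reply is that ILD ordinarily includes pneumonitis, and SAP Section 8.3.4 classes non-infectious pulmonary toxicities by the Broad ILD SMQ. That reading is reasonable, but the SAP definition governs analysis, not dosing. The hold sentence lists the two as alternatives, and the stop sentence then keeps only one.

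A third reply is that other safeguards exist. Events meeting seriousness criteria reach the sponsor within 24 hours (Section 7.8.1.4), and the IDMC reviews safety quarterly (Section 9.4.12). These make sponsor contact before re-dosing more likely, but they are reporting paths. Unacceptable toxicity and physician decision (Section 5.3) are grounds for stopping, but they are discretionary and not event-specific.

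Finally, the Grade 2 lines are not true contradictions, since a statement that no modification is required does not forbid a hold. That is correct, and they are counted separately for that reason.

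**Conclusion.** The concern holds. As written, the residual row contradicts two stop rules, for confirmed symptomatic heart failure and confirmed related ILD at Grade 3, and the pulmonary stop sentence leaves Grade 2–3 pneumonitis without an explicit stop. All the texts agree on the initial hold at Grade 3; they part only after confirmation. Grade 4 is unaffected.

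The conclusion rests on a literal reading of the row label and on the absence of any precedence statement. The practical size is small: 0.1 to 1 expected event per 100 subjects under the assumed range, with fewer subjects mis-dosed and no figure available for how many. Because the error runs towards re-exposure after drug-related cardiac or lung toxicity, and the 4-week contact rule would not reliably catch it, it should be corrected. The safety rules themselves exist; what is missing is a complete exclusion in the general row and consistent wording in the pulmonary paragraph.

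**What to change.** Make three edits in Protocol Section 5.2.3:

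1. Extend the exclusion in the label of the last row of Table 7 to *other than IRR, left ventricular dysfunction/heart failure, and pneumonitis/ILD*.
2. Extend footnote a so that it also points to Table 8 and to the Pulmonary Toxicity text.
3. Add *pneumonitis or* before ILD in the pulmonary stop sentence, so that it covers the same events as the hold sentence.

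The cost is one label, one footnote and two words, issued in a protocol amendment or clarification letter. No new data or procedure is needed.
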